Our primary research questions ask to what extent the offer to watch *Plan A* relative to the offer to watch *The Toxic Life Cycle of a Cigarette* impacts participants' reported: 1) use of LARC; 2) times having sex without a condom; and 3) receipt of STI testing three months after receiving the treatment. We describe below the specific operationalization of each of these three primary outcome measures.

i. LARC Use

LARC use is constructed as a dichotomous variable – participants are either coded as currently using a LARC or not currently using a LARC. Data used to assess the impact of the treatment (*Plan A*) on LARC use are obtained from the following item on the *Participant Questionnaire*, which is administered to both the treatment and control groups at baseline and three months post-baseline.

- *Which of the following methods of prescription birth control are you currently using?*
 - *None: I am not currently using any of these methods*
 - *Oral contraceptives (for example, the pill)*

- *The patch (for example, Ortho Evra)*
- *The shot/injection (for example, Depo-Provera)*
- *The ring (for example, NuvaRing)*
- *The implant (for example, Implanon or Nexplanon)*
- *IUD (for example, ParaGard, Skyla, or Mirena)*

Persons who indicate that they are currently using either *The implant* or *IUD* are considered to be currently using LARC and are coded as 1. Persons who select *None*, *Oral contraceptives*, *The patch*, *The shot/injection*, or *The ring* are considered to not be currently using LARC and are coded as 0.

Plan A will be considered to have a positive impact on LARC use if, as compared to participants who are assigned to the control group, a larger proportion of participants who are offered *Plan A* report using LARC at the three-month follow-up and the difference between groups is statically significant.

ii. Times having sex without a condom

We operationalize times having sex without a condom as a risk outcome; that is, we measure the frequency with which participants engage in the risk behavior of having sex without a condom, rather than the frequency with which they engage in the safe sex practice of using condoms. Constructing the variable in this way allows us to examine the self-reported sexual behaviors of the full analytic sample of participants, regardless as to whether or not they are sexually active.

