³⁹ With the assumption that we maintain low attrition and differential attrition and that the study otherwise executes the RCT with integrity, we should be able to estimate an un-biased estimate of the average treatment effect of the intent to treat participants with *Plan A* by comparing differences in the means of the outcome variable reported by the treatment group with those reported by the control group. We could then provide a compelling response to our research question by testing the hypothesis that there is no difference between the two groups using straight-forward hypothesis testing statistics (t-test). With that said, we propose a regression-based model that includes covariates, because randomization should ensure covariates are uncorrelated with the treatment variable (i.e., they should not affect the estimate of the treatment effect), and in the instance they are significant predictors of the outcome, their inclusion in a regression model will decrease the standard error of the estimates, making them more precise. See: Angrist, J. D., & Pischke, J. (2009). *Mostly harmless econometrics: An empiricist's companion*. Princeton: Princeton University Press; Rosenblum, M. and van der Laan, M. J. (2009), Using Regression Models to Analyze Randomized Trials: Asymptotically Valid Hypothesis Tests Despite Incorrectly Specified Models. *Biometrics*, 65: 937-945. doi:10.1111/j.1541-0420.2008.01177.x.

effect of the treatment, we propose a model-based approach because it will increase the precision of those estimates. The empirical model will be estimated with an OLS regression (using Stata).⁴⁰ We present the empirical model here:

$$Y_{Post} = \beta_0 + \beta_1 T + \beta_2 Y_{Pre} + \sum (\beta_p X_p) + \varepsilon$$

Where:

Y_{Post} – The outcome variable of interest, either: 1) times having sex without condoms in the past 3 months (continuous; values range 0 to k , where 0= has had sex without condoms 0 times in past 3 months, and k = number of times having sex without condoms in past 3 months); 2) current LARC use (0= not currently using a LARC; 1= currently using a LARC); or 3) STI testing in the past 3 months (0=not tested for STIs/STDs in past 3 months; 1= tested for STIs/STDs in past 3 months) reported by participant i at the 3-month follow-up. (see Table 1 for full details on the variable construction).

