⁴⁰ If the outcome measure is dichotomous, we will also construct a linear probability model to confirm our benchmark results. Beyond this, as part of our sensitivity analyses, we will construct a logistic regression model to explore any potential differences in our effect estimates given the model utilized.

⁴¹ Sites currently participating in the study have been organized into four regions for administrative and staffing purposes.

treatment and control participants' self-reported times having sex without condoms in the past three months at the three-month follow-up; 2) the adjusted odds ratio comparing treatment participants' current LARC use to control participants' use at the three-month follow-up; or 3) the adjusted odds ratio comparing treatment participants' STI testing in the past three months to control participants at the three-month follow-up.

ε – The error term or unexplained individual-level variance that remains for each observation after the structural components of the model are estimated. It is the difference between the observed and the predicted values at the individual level.

We will report model-estimated effects and the results of significance tests in the findings section of the final impact report. Statistical significance will be based on test statistics produced by Stata for the coefficient β_1 using a two-tailed test, with $p < .05$.

- ii. **Sample attrition:** Overall and differential attrition will be calculated using the full sample of participants enrolled in the study. This will be determined using data within the *Participant Dataset*. We will calculate overall attrition using the following formula:

$$Attrition_{participant} = 1 - \left(\frac{Assessed_{participant}}{Base_{participant}} \right)$$

where:

$Attrition_{participant}$ - the proportion of participants enrolled in the study who did not complete a 3-month follow-up questionnaire

$Base_{participant}$ - the number of participants enrolled into the study

$Assessed_{participant}$ - the number of participants who completed a 3-month follow-up questionnaire

Differential attrition will be calculated using the following formulas:

$$Attrition_{participant\ C} = 1 - \left(\frac{Assessed_{participant\ C}}{Base_{participant\ C}} \right)$$

$$Attrition_{participant\ T} = 1 - \left(\frac{Assessed_{participant\ T}}{Base_{participant\ T}} \right)$$

$$Differential\ Attrition_{t-c} = abs(Attrition_{participant\ T} - Attrition_{participant\ C})$$

Where:

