$Differential\ Attrition_{t-c}$ - the absolute difference between the proportion of treatment group participants who did not complete a 3-month follow-up questionnaire and the proportion of control group participants who did not complete a 3-month follow-up questionnaire

$Attrition_{participant\ C}$ - the proportion of participants enrolled in the study and randomly assigned to the control group who did not complete a 3-month follow-up questionnaire

$Base_{participant\ C}$ - the number of participants enrolled into the study and randomly assigned to the control group

$Assessed_{participant}C$ - the number of participants randomly assigned to the control group who completed a 3-month follow-up questionnaire

$Attrition_{participant}T$ - the proportion of participants enrolled in the study and randomly assigned to the treatment group who did not complete a 3-month follow-up questionnaire

$Base_{participant}T$ - the number of participants enrolled into the study and randomly assigned to the treatment group

$Assessed_{participant}T$ - the number of participants randomly assigned to the treatment group who completed a 3-month follow-up questionnaire

Overall and differential attrition will be reported in the findings section of our final impact report.

iii. **Adjustments for multiple comparisons:** Following guidance provided under the grant for our impact analysis plan,⁴² we will adjust for multiple comparisons in all of our primary outcomes analyses, regardless of outcome domains. We propose to use the Benjamini-Hochberg method.⁴³ This method controls for the false discovery rate (FDR), which is the expected value of the number of false positive tests divided by the total number of significant tests within a family of tests. The following procedures will be used to implement this adjustment:

1. The p-values generated by our models of the effect of the intervention on our three primary outcome measures will be ranked from smallest to largest, indexed by i (where $i = 1$ for the smallest p-value and $i = k$ for the largest p-value).

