⁴³ This method has been selected because it helps to control the Type 1 error rate without also increasing the Type 2 error rate, which in our view is a serious consideration in preliminary efforts to identify evidence of effectiveness of new approaches. Benjamini, Y., & Hochberg, Y. (1995). Controlling the false discovery rate: a practical and powerful approach to multiple testing. *Journal of the royal statistical society. Series B (Methodological)*, 289-300.

imputing or adjusting for missing data; (3) excluding unreliable data; (4) including outliers; and (5) condensing data collection windows to exclude late responders; and (6) using an alternative model specification to estimate program effects.

1. **Without baseline covariates.** Our benchmark approach is to include baseline covariates in our model to improve the precision of our estimates. To test this, we will conduct sensitivity analyses that involve running identical empirical models without the covariates included. Analytic findings for both approaches will be presented alongside each other in an appendix of the impact report.
2. **Without adjusted baseline data.** As outlined in the *Missing data approach* section, our benchmark approach is to adjust baseline data as published guidance suggests that this may produce unbiased impact estimates and maximize the use of available data. We will test this by way of sensitivity analyses that involve running identical empirical models without the adjusted data. Analytic findings for both approaches will be presented alongside each other in an appendix of the impact report.

As outlined in the *Baseline equivalency* section, we will also produce diagnostic estimates of baseline equivalency on the pre-intervention outcome variables according to our benchmark approach and the sensitivity study alongside each other in an appendix of the report.

3. **With unreliable data.** As discussed in the *Data cleaning* section, data for cases that are deemed unreliable are treated as *unit missing* and excluded from benchmark analyses. To test this, we will conduct sensitivity analyses that involve running identical empirical models with the unreliable data included. Analytic findings for both approaches will be presented alongside each other in an appendix of the impact report.

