4. **Without outliers.** As discussed in the *Data cleaning* section, extreme data values are investigated and flagged as outliers. Our benchmark analytic approach is to include data flagged as outliers (i.e., extreme values that are not considered invalid) in analysis. We will also conduct sensitivity analyses that exclude these data and report substantive differences in the results section of the report.
5. **Condensed data collection windows.** Our benchmark approach is to include follow-up data from all participants who completed a questionnaire during their open data collection window, regardless of the time point in that window when it was completed. Data collection windows are broad to minimize attrition from the analytic sample. To examine whether or not this influences our results – and, in particular, whether or not study participants who respond later report different outcomes from those who respond earlier – we will conduct an analysis that examines the difference, if any, in response time between treatment and control participants and compares impact estimates for analytic samples without late responders. Late responders will be defined as those participants who complete their three-month questionnaire more than one month after the initiation of the three-month data collection window.
6. **Statistical Modeling.** We have proposed using OLS regression as the benchmark statistical model we intend to use to estimate the program’s effect on the primary outcomes. OLS is robust in large samples to misspecification. OLS is also a conventional approach to modeling dichotomous and count outcomes in evaluation because it produces estimates that are more immediately and readily interpretable, and because it tends to produce results that are substantively identical to the models that technically fit the data better. We will conduct tests that test the validity of this assumption and if there is a

substantive difference in point estimates of interest produced by OLS and logit (or variant of – e.g. Firth logit) or statistical count models (e.g. Poisson and negative binomial families), we will report results of the models that fit the distributional characteristics of the data better (based on diagnostics and log-likelihood statistics).

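### The OLS coefficient is labelled an odds ratio for two binary primary outcomes, and sensitivity item 6 leaves open which model's result decides

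*SAP*

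**What the plan says.** Section 4f.i writes one linear equation with an additive error term for all three primary outcomes, two of them coded 0/1, and states: "The empirical model will be estimated with an OLS regression (using Stata". Section 4f.iv item 6 repeats the choice: "We have proposed using OLS regression as the benchmark statistical model we intend to use to estimate" the effect on the primary outcomes.

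Section 4f.i then gives the meaning of the treatment coefficient, β1. For the condom outcome it is an adjusted mean difference. For LARC use and for STI testing it is "the adjusted odds ratio comparing treatment participants" with controls. Footnote 40 adds: "If the outcome measure is dichotomous, we will also construct a linear probability model to confirm our benchmark results". It places logistic regression among the sensitivity analyses.

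The success criteria in section 4a for the two binary outcomes ask for "a larger proportion of participants who are offered" Plan A to report the behaviour, with a significant difference.

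Item 6 also sets a trigger, a "substantive difference in point estimates of interest produced by OLS and logit" (or a count model). If it is met, the SAP will report whichever models fit the data's distribution better, judged on diagnostics and log-likelihood. Section 4f.iii, step 1, takes its inputs from an unspecified set of models: "The p-values generated by our models of the effect of the intervention on our three primary outcome measures will be ranked".

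**The concern.** There are two linked defects.

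First, the estimator and the stated estimand do not match. OLS cannot return an odds ratio, and even a logit coefficient is a log odds ratio. An author following the definition of β1 would either mislabel a risk difference or report a different model from the one declared as benchmark. Footnote 40 adds to the doubt, because the linear probability model offered as confirmation is the same OLS fit.

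Second, item 6 ties the reported model to the treatment estimates themselves. It does not define what counts as substantive, does not say on which scale a mean difference is compared with a rate ratio, and lists the alternative models only by example. It also does not say whether the better-fitting model replaces OLS for the primary conclusion or for Benjamini-Hochberg. At stake are the effect measure for two primary outcomes and, for the third, whether the primary test is fixed before the results are known. Section 4g carries the same approach to the secondary outcomes.

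**Working it through.** **Binary outcomes: what β1 is.** With Y coded 0/1 and E(Y) linear in treatment T and the covariates, β1 = p_T − p_C at fixed covariates. The odds ratio is [p_T/(1−p_T)] / [p_C/(1−p_C)]. The SAP gives no expected rates, so these are assumed:

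| p_C | p_T | Risk difference | Odds ratio |
|---|---|---|---|
| 5% | 8% | 0.03 | 1.65 |
| 10% | 14% | 0.04 | 1.47 |
| 20% | 25% | 0.05 | 1.33 |
| 50% | 56% | 0.06 | 1.27 |

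Fitting both models to 885 per arm (1,770/2) with 88 and 124 events gives OLS β1 = 36/885 = 0.041, p = 0.0084. Logit gives an odds ratio of (124/761)/(88/797) = 1.476, p = 0.0087. The reported number and its null value change; the p-value barely does.

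Section 4d, step 1, agrees with this reading. It uses a linear probability model for dichotomous baseline measures, calls it a variation of the impact model, and reads its β1 as an adjusted mean difference.

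**Binary outcomes: does the verdict move?** OLS and logit were fitted with treatment and the baseline outcome, with assumed n = 1,450 and 4,000 runs per setting.

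- LARC-like (baseline 12%; follow-up 80% in users, 10% in non-users): 1 discordant verdict under the null, 9 with a 0.12 SD effect.
- STI-like (baseline 45%; follow-up 60% and 45%): 0 and 0.
- Largest p-value difference: 0.0015.
- Median LARC coefficients on their native scales: 0.047 (OLS) and 0.42 (logit). A comparison of point estimates has no meaning until they are put on one scale.

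**Count outcome: item 6 as a rule.** Item 6 has to be given a form before it can be tested. The form assumed here is: switch to negative binomial (NB) if |NB average marginal difference − OLS β1| / |OLS β1| exceeds a threshold and the NB log-likelihood is higher. There were 5,000 null runs per setting with n = 1,450; the Monte Carlo standard error is √(0.05 × 0.95/5,000) ≈ 0.3 points. Setting A is zero-inflated (25.6% zeros, mean 16.1, SD 26.5). Setting B is gamma-Poisson (mean 15.0, SD 19.7).

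| Threshold | 10% | 25% | 50% | 100% |
|---|---|---|---|---|
| A: model switched | 90% | 75% | 55% | 32% |
| A: verdict changed by the switch | 3.9% | 2.9% | 2.0% | 0.6% |
| A: type I error | 6.4% | 7.1% | 6.9% | 5.4% |
| B: type I error | 5.6% | 6.4% | 5.7% | 5.1% |
| A, NB effect at covariate means | 4.9% | 4.4% | 5.0% | 4.9% |
| B, NB effect at covariate means | 4.6% | 4.4% | 5.0% | 4.9% |

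For reference, OLS alone gives 4.8% (A) and 4.9% (B), and NB alone 5.7% and 5.0%. NB had the higher log-likelihood than OLS in 100% of runs, so the fit criterion never kept OLS; only the undefined trigger did. Further assumed counts gave about 7–9% on the average-marginal scale and 5–7% at covariate means.

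**Count outcome: a real effect.** A 20% reduction is 0.2 × 16.1/26.5 = 0.12 SD in A and 0.2 × 15.0/19.7 = 0.15 SD in B. Over 2,000 runs each, OLS and NB disagreed on significance in 9.5% (A) and 4.8% (B) of trials. The further assumed counts gave 5.5–16.5%.

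**Which alternative is chosen matters too.** In 400 null runs with N = 1,770 and assumed NB counts (mean 12, size 0.4), rejection was 4.5% for OLS, 5.3% for NB and 71% for Poisson with model-based standard errors. OLS and NB disagreed in 0.8% of runs.

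**The case against.** The mislabel moves no verdict, and the estimator itself is not really in doubt: item 6 defends OLS for dichotomous and count outcomes, and footnote 40 assigns logit to sensitivity analysis. That is right, and it confines the first defect to what is reported. It is also fair that asking for a larger proportion is a directional criterion, which an odds ratio above 1 would meet as well; the criterion fits a risk difference but does not by itself identify one.

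On item 6, section 4f.i bases significance on the test statistic for β1, the coefficient of the OLS equation, and item 6 sits under a heading about testing the benchmark. The natural reading is therefore that OLS p-values enter Benjamini-Hochberg. This narrows the gap without closing it, since item 6 says the better-fitting model's results will be reported and never says in what role. Items 1–3 promise that "Analytic findings for both approaches will be presented alongside each other in an appendix of the impact report"; item 6 does not. Items 4 and 5 lack those words as well, so their absence alone is weak evidence of replacement.

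The fit criterion does restrain something: it preferred NB to Poisson in 300 of 300 runs per setting, which rules out the most dangerous listed option. It does not restrain the choice between OLS and NB.

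Finally, the simulated rule is an assumption. Dividing by an OLS estimate near zero under the null raises the switching rates, and the error rates are for one test at 0.05, not carried through Benjamini-Hochberg. Both limits stand.

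**Conclusion.** The concern holds on both parts. The definition of β1 contradicts the declared OLS benchmark for two of the three primary outcomes, and footnote 40's confirmation repeats the benchmark. This needs no assumption. Its consequence is a wrongly described effect measure with the wrong null value, not a changed conclusion.

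Item 6 leaves the role of the alternative model, and the trigger for it, unspecified. Its effect on the condom outcome depends on count distributions, a sample size and a switching rule that the SAP does not give. Under those tried, type I error ranged from no inflation to about 9%, depending on threshold and scale. Inflation is thus plausible, generally modest, and can vanish. The firmer point is that with a true 20% reduction the two models disagree on significance often enough, about 5% of trials or more, for an unfixed choice to decide a primary conclusion. This should be corrected before analysis, though it does not threaten the design.

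**What to change.** - In section 4f.i, define β1 for LARC use and STI testing as the adjusted risk difference.
- Correct footnote 40: the benchmark is itself the linear probability model, and logit is the sensitivity analysis.
- In section 4f.iii, state that only the OLS p-values enter Benjamini-Hochberg and determine the primary conclusions.
- In section 4f.iv item 6, state that logit and count-model results are always reported beside OLS, converted to marginal differences so that the scales match, and never replace it.

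Naming one model per outcome in advance would also close the gap; keeping OLS throughout is the smaller change because the SAP already declares it. The cost is SAP wording only, since every model is already planned. The one thing given up is the freedom to lead with a better-fitting model after seeing the estimates.

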Video Health Study: Analysis Plan

U.S. Department of Health and Human Services
Office of Adolescent Health
Evaluation of “Plan A”
NCT Number NCT03238313

January 2019

The Policy & Research Group
[name]
[name]
www.policyandresearch.com
[contact]

INTRODUCTION: STUDY CHANGES TIMELINE

OVERVIEW

On April 4th, 2019, The Policy & Research Group reviewed the registry page for the *Evaluation of “Plan A”* on clinicaltrials.gov and found several inaccuracies in language and content. Updates were made to the registry to reflect the study design documented in our Evaluation Abstract (see Appendix B),¹ submitted to the Office of Adolescent Health on September 18, 2017 and the Impact Analysis Plan (included below), submitted to OAH on January 31, 2019.

In an effort to be transparent about changes that have been made to the registry since its inception, we outline below substantive changes that have been made to the design of the study over the course of the implementation period. Changes are organized chronologically. Detail is provided on what the original content of the Clinical Trials registration included, what the revised content now indicates, and (when applicable) provides a rationale for the change.

JULY 2017

- Office of Adolescent Health (OAH) Teen Pregnancy Prevention (TPP) Tier 2B grantees receive notice that the funding period for the grant has been shortened by two years, shifting the end date of the grant from June 30, 2020 to June 30, 2018

SEPTEMBER 2017

- Change in the target sample size from 2,250 to 1,770. After reviewing enrollment trends, in consult with the grant Evaluation Technical Liaison and Program Officer, the decision was made to revise enrollment estimates. Baseline data gathered from the current study were used to update power calculations in order to estimate the sample size needed to detect hypothesized programmatic effects; the revised enrollment target reflects the minimum sample required to detect small program effects (MDES = .12).

APRIL 2018

- Federal judge rules in favor of the OAH TPP Tier 2B grantees and funding is reinstated. Funding period will now end on June 30, 2020.

OCTOBER 2018

- Estimated Primary Completion Date changed from October 31, 2018 to May 31, 2019 to provide sufficient time to reach target sample size
- Estimated Study Completion Date changed from November 30, 2019 to June 30, 2020 to provide sufficient time to complete follow-up period

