STI testing is constructed as a dichotomous variable – participants are either coded as having been tested for STIs in the past three months or not tested.¹² Data used to assess the impact of the treatment (*Plan A*) on STI testing are obtained from the following two items on the *Participant Questionnaire*, which is administered to both the treatment and control groups at baseline and three months post-baseline.

- The first question asks: *To the best of your knowledge, have you ever been tested for other sexually transmitted infections/diseases (STIs/STDs), such as chlamydia or gonorrhea?*
- If respondents select *Yes* to the first question, they are then asked this second question: *Have you been tested for STIs/STDs other than HIV in the past 3 months?*

Persons who select *Yes* to the second question are coded as 1, indicating that they have been tested for STIs/STDs other than HIV in the past 3 months. Persons who select *No* to the first and/or second questions are considered to not have been tested and coded as 0.

Plan A will be considered to have a positive impact on STI testing if, as compared to participants who are assigned to the control group, a larger proportion of participants who are offered *Plan A* report STI testing at the three-month follow-up and the difference between groups is statically significant.

Secondary outcome measures

Our secondary research questions ask to what extent the offer to watch *Plan A* relative to the offer to watch *The Toxic Life Cycle of a Cigarette* impacts participants' reported: 1) use of dual methods of protection (condom and prescription birth control use) during vaginal sex; and 2) use of other effective contraceptive methods (pill, patch, ring, or Depo-Provera) three months after receiving the treatment. We describe below the specific operationalization of each of these two secondary outcome measures.

i. Use of dual methods of protection

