$Base_{participant\ T}$ - the number of participants randomly assigned to the control group

$Received_{participant\ T}$ - the number of participants randomly assigned to the control group who received the *Plan A* video

Levels of crossover and contamination will be reported in the findings section of our final impact report.

- f. **Analytic approach for primary research questions:** As detailed in our primary research questions, this study investigates whether offering *Plan A* to participants impacts their reported LARC use, number of times having sex without condoms, and STI testing. We do this within the intent to treat (ITT) framework, which does not measure the effect of the participant’s exposure to the treatment itself but rather the effect of the offer of the treatment relative to the offer of receiving the control condition. This framework maintains the integrity of the experimental structure by including all participants who were randomized (except those who attrite) in the analytic sample, thereby maintaining an exogenous assignment of participants to experimental condition. Bias can be insinuated, however, through self-selection if any participant who is randomized fails to provide outcome data.
- i. **Model specification and covariates:** The primary research questions under investigation in this study are whether offering *Plan A* to participants impacts their: (1) reported use of LARC, (2) times having sex without condoms, and (3) reported STI testing partners (see Table 1 in Appendix A for variable constructions). We propose to estimate these impacts using a regression that will model intervention effects as a function of assignment to *Plan A* (i.e., Treatment), relevant baseline covariates, a baseline measure of the outcome variable, and regional (blocking) indicators (see Table 2 in Appendix A for variable constructions).³⁹ Although a straight difference-of-means approach should provide unbiased estimates of the

³⁸ In the OAH Impact Analysis Plan guidance for Cohort 2 Tier 2B grantees, contamination is described as occurring “when individuals assigned to the counterfactual condition end up receiving all or portions of the conditions intended only as part of the intervention.” Given this, we calculate contamination in our sample as participants assigned to the control condition who received any amount of the *Plan A* video, as this is the intended treatment condition.

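### Log-likelihood cannot decide between OLS and logit or Firth logit for the binary outcomes, and the plan does not state the scale on which their estimates are compared

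*SAP*

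**What the plan says.** Section 4f.i sets the benchmark for the primary outcomes: "The empirical model will be estimated with an OLS regression (using Stata"). Two of the three are binary: "LARC use is constructed as a dichotomous variable" and "STI testing is constructed as a dichotomous variable" (section 4a). The model includes treatment, baseline covariates, "a baseline measure of the outcome variable, and regional (blocking) indicators".

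Footnote 40 adds, for dichotomous outcomes, that "we will construct a logistic regression model to explore any potential differences in our effect estimates given the model utilized". Item 6 of section 4f.iv goes further. If there is a "substantive difference in point estimates of interest produced by OLS and logit" (or a Firth variant, or count models), then "we will report results of the models that fit the distributional characteristics of the data better (based on diagnostics and log-likelihood statistics". The diagnostics are not named and no size of difference is given.

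Two other places matter. The definition of β1 in section 4f.i calls it an adjusted odds ratio for LARC use and STI testing, although the fitted model is OLS, whose coefficient for a 0/1 outcome is a difference in proportions. Section 4g carries the same approach to the secondary outcomes, one of which (use of other effective contraceptive methods) is also binary.

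**The concern.** Item 6 is listed as a sensitivity analysis, but it can decide which estimate is reported for a primary outcome. The primary p-values also feed the Benjamini-Hochberg ranking in section 4f.iii, so a switch could carry into it. The criterion therefore has to measure what it claims to measure.

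Log-likelihood is the only statistic that item 6 names, and between these models it is not on a common footing:

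- **OLS:** a Gaussian density, with no upper bound, which depends on the units of the outcome.
- **Logit:** a Bernoulli probability, so its log is never above 0.
- **Firth logit:** a likelihood with a penalty term added, comparable with neither.

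The trigger has a related gap. It compares point estimates without saying on what scale, and the odds-ratio wording for β1 adds to the uncertainty. At stake is a report that calls its chosen estimate the better-fitting one on a number that does not measure fit.

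**Working it through.** The SAP states no figure here, so there is none to reproduce. It gives the sample-size target ("Change in the target sample size from 2,250 to 1,770") but no prevalence and no R². Those are assumed below and shown as ranges.

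**1. Identical fits, no covariates.** With prevalence p, both models fit p to everyone. Log-likelihood per woman:

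- Gaussian: -0.5 × [ln(2πp(1-p)) + 1]
- Bernoulli: p ln p + (1-p) ln(1-p)

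At p = 0.10, the Gaussian value is -0.5 × [ln(0.5655) + 1] = -0.215. The Bernoulli value is 0.1 × (-2.303) + 0.9 × (-0.105) = -0.325. The gap is 0.110 per woman.

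| Prevalence | Gaussian | Bernoulli | OLS minus logit, 1,770 women |
|---|---|---|---|
| 0.02 | 0.547 | -0.098 | +1,142 |
| 0.10 | -0.215 | -0.325 | +195 |
| 0.15 | -0.389 | -0.423 | +60 |
| 0.20 | -0.503 | -0.500 | -4 |
| 0.30 | -0.639 | -0.611 | -49 |
| 0.40 | -0.705 | -0.673 | -57 |
| 0.50 | -0.726 | -0.693 | -58 |

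The sign changes at p = 0.196 (by symmetry also at 0.804), although the two fits are the same throughout. Coding the outcome 0/100 instead of 0/1 moves the OLS log-likelihood by -1,770 × ln 100 = -8,151 and changes nothing about the fit.

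**2. Identical fits, with a baseline outcome.** Take a model saturated in treatment and a 0/1 baseline outcome. OLS and logit then give equal fitted probabilities by construction. With cell weights w and probabilities p, the residual variance is s² = Σ w p(1-p). The Gaussian total is -0.5N[ln(2πs²) + 1], and the Bernoulli total is N Σ w[p ln p + (1-p) ln(1-p)], with N = 1,770.

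| Baseline users | Outcome among users / non-users (control) | Added by treatment | Prevalence | R² | OLS minus logit |
|---|---|---|---|---|---|
| 10% | 80% / 5% | 3 points | 0.14 | 0.42 | +312 |
| 10% | 80% / 20% | 3 points | 0.28 | 0.16 | -14 |
| 30% | 85% / 15% | 4 points | 0.38 | 0.44 | +46 |
| 30% | 60% / 40% | 4 points | 0.48 | 0.04 | -57 |
| 50% | 85% / 15% | 0 | 0.50 | 0.49 | +60 |

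So prevalence alone does not fix the sign. Residual variance does: prevalence together with how strongly baseline predicts follow-up.

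**3. Does the criterion find the true model?** Simulation with 1,770 women, 200 runs per setting, treatment and one continuous covariate:

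| True model | Prevalence | OLS chosen by reported log-likelihoods | OLS chosen when both fits are scored by the Bernoulli likelihood |
|---|---|---|---|
| Logistic | 0.08 to 0.17 | 99.5 to 100% | 0 to 3% |
| Logistic | 0.25 to 0.33 | 0% | 0.5 to 3% |
| Logistic | 0.53 | 0% | 21% (fits nearly equal) |
| Linear | 0.08 to 0.17 | 100% | 75 to 84% |
| Linear | 0.27 to 0.50 | 0% | 87 to 91% |

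OLS fitted values were truncated to 0.001 to 0.999 for the common score. The reported log-likelihoods choose essentially the same model whichever is true. The common score follows the truth.

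**4. Scale of the trigger.** For 20% against 25%, the difference in proportions is 0.25 - 0.20 = 0.05. The log odds ratio is ln[(0.25/0.75)/(0.20/0.80)] = 0.288. These describe the same effect.

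**5. Practical effect.** In simulated trials, the OLS coefficient and the logit average marginal effect for treatment differed by at most 0.002, and significance disagreed in at most 1% of runs.

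**The case against.** The case on the other side has four parts, and much of it stands.

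**Direction.** A reader might infer that the rule keeps OLS for rare outcomes and replaces it with logit for common ones. The documents do not support that. Every benchmark model contains the baseline outcome, and LARC use may well persist. In simulations of 1,500 women with a strongly predictive baseline (assumed 85 to 90% of baseline users still using, 10 to 15% of others), OLS came out ahead in every run at prevalences of 32 to 46% (R² 0.46 to 0.52). With R² near 0.03 it never did at 40 to 52%. Without prevalence and R², no direction can be claimed.

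**Trigger.** A reader might also infer that raw coefficients will be compared, so that the trigger always fires. The SAP does not say so. Item 6 expects OLS to agree in substance with better-fitting models, which makes sense only on a comparable scale. What stands is that the scale is left unstated and that β1 is described inconsistently with the fitted model.

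**Other criteria.** Item 6 also cites diagnostics, does not rule out scoring OLS fits on the Bernoulli scale, and covers count models, where likelihood can properly compare Poisson with negative binomial. This is fair, but no common score is specified, and the log-likelihood that OLS software ordinarily reports is the Gaussian one.

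**Consequence.** On a common scale, OLS and the logit marginal effect nearly coincide under 1:1 randomisation, so the switch would rarely be reached. This stands, and it limits the severity.

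**Conclusion.** The concern holds as a minor point. Between OLS and logit or Firth logit, log-likelihood is not a valid criterion for the two binary primary outcomes or for the binary secondary outcome. With identical fits, the artefact ranges from hundreds of units in favour of OLS to about 58 against it, across assumed prevalences and baseline associations. The choice follows residual variance and not fit.

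It should not be read as showing that trial conclusions would change. The expected effect on significance is small. The harm is an arbitrary choice of reported primary estimate, described as better fitting without evidence.

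The incomparability of the likelihoods needs no assumption about the data. The sizes rest on assumed prevalences and baseline associations, and on the OLS log-likelihood being the Gaussian one. The count outcome was not tested.

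**What to change.** In section 4f.iv, item 6:

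1. Delete log-likelihood as a criterion between OLS and logit or Firth logit.
2. Define the triggering difference on one scale: the OLS coefficient against the average marginal effect (adjusted difference in proportions, or in mean counts) from the logit or count model. State how large a difference counts.
3. If fit is to be described, score both models' fitted probabilities with one measure, such as the Brier score, and add a calibration check.
4. Keep likelihood or AIC for comparisons within a family, such as Poisson against negative binomial.

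In section 4f.i, make the description of β1 for binary outcomes agree with the OLS model.

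The cost is a few sentences and a standard marginal-effects command, with no new data. If a Bernoulli log score is used instead of the Brier score, OLS fitted values outside (0,1) must be truncated.
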